## 6 Investigational Medicinal Products

### 6.1 Treatment Regimen

Participants will be randomized to their initial migraine prevention medication. Participants must receive the first dose of their allocated medication at the Baseline Visit (Visit 2). However, during the remainder of the study observation period, treatment choices will be based upon the treating clinician's judgement and the participant's preference (See Section 6.3.1 below for more details). No additional direction will be given by the CRO or the study sponsor. However, any participant wishing or needing to switch to an alternate medication outside of the study-specific guidelines for doing so, as described in Section 6.3.1, will need to be withdrawn from the study. Participants switching to an advanced preventive medication other than their initially assigned treatment in accordance with Section 6.3.1 will be permitted to remain in the study. There will be no restrictions on the use of other migraine related medications during the study period for acute or preventive treatment if those medications are prescribed by the participant's treating physician. However, products purchased with study-specific vouchers cannot be used for an off-label indication. Participants must meet the criteria for CM at baseline in order to be randomized to onabotulinumtoxinA (Botox®). Any changes in migraine preventive medications, prescribed or OTC, will be reported in the smartphone application by the participant. The reason for any treatment change will be

---

investigated by the study coordinator and recorded in the CRF. Any adverse events identified as the cause of a medication switch (e.g. lack of efficacy) will be reported according to Section 10.3.

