#### **5.5 Withdrawal Criteria**

Information on participants who withdraw from the study will be collected in the withdrawal section of the CRF.

A participant must be withdrawn from the study if:

- the participant withdraws their consent (defined as a participant who explicitly takes back their consent); section [8.9](#) states how the patient's data will be handled
- the participant is lost to follow-up (defined as a participant who fails to comply with scheduled study visits or contact, who has not actively withdrawn from the study, and

for whom no alternative contact information is available [this implies that at least two documented attempts have been made to contact the patient])

- the investigator considers it, for safety and/or study compliance reasons, in the best interests of the participant that they be withdrawn from treatment
- All participants will be permitted to withdraw at their choice or upon advice of their treating physician. Information collected from the participant prior to withdrawal will remain in the study data set.

No participant will be withdrawn from the study due to non-compliance with treatment. As this is a pragmatic real-world study, the failure to comply with treatment is considered a real-world outcome. However, an investigator may withdraw a participant from the study based upon their medical judgement if they deem continued involvement in the study is detrimental to the participant's welfare.

Products purchased with study-specific vouchers cannot be used for an off-label indication. Participants must meet the criteria for CM at baseline in order to be randomized to onabotulinumtoxinA (Botox®). Participants who do not comply with this requirement will be withdrawn from the study.

Participants who become pregnant will be withdrawn from the study and counselled to enroll in the Lundbeck pregnancy registry. The Lundbeck pregnancy registry is a prospective, observational study in the United States that will be initiated prior to the end of this trial.

Participants who withdraw will not be replaced.

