#### **6.3.1 Change in Treatment**

Participants may switch to an alternative preventive treatment in either treatment cohort after they have received their initial treatment with the medication to which they were randomized. Such a decision may be made upon recommendation of their treating clinician or participant preference. The site staff will investigate the reason for treatment change with both the treating clinician and participant. The use of medications, including gepants, for relief of acute migraine symptoms in either treatment arm is permitted and will be recorded in the smartphone application.

For all participants, the treatment to which they are initially assigned must be the treatment given at Baseline (Visit 2). Switching of medication is not permitted prior to administration of the first dose of medication. For participants who receive eptinezumab or Botox as their initial treatment and elect to switch to a subcutaneous anti-CGRP injectable (i.e., erenumab, fremanezumab or galcanezumab), they may not do so until week 12 (visit 5), after the treatment window for their initial treatment has ended. Participants who receive eptinezumab or Botox at week 12 (Visit 5) will not be permitted to switch their treatment for the remaining duration of the study.

Participants initially treated with a subcutaneous anti-CGRP injectable may only switch to eptinezumab, or Botox at week 12 (visit 5) due to the design of the study. However, these participants may switch to another of the subcutaneous anti-CGRP injectable medications at any time, once the treatment window for their previous injection has ended.

No changes in treatment will be permitted after Visit 7.

All changes in treatment are to be documented in the eCRF.

If a participant wishes to switch their medication, but does not meet the specified criteria to do so, as stated above, they should be withdrawn from the study and be treated as per standard of care by their physician.

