### **8.9 Withdrawal Visit**

Participants who withdraw from the study prior to Visit 8 will be asked to complete an Early Termination Visit, if at all possible. The visit must be scheduled as soon as possible after withdrawal. All information collected at an Early Termination Visit is to be recorded in the Visit 8 forms of the eCRF.

In addition, all assessments normally scheduled to be completed by the participants at Visit 8 in the eDiary ([Panel 3](#)) will be completed on the day of the Early Termination Visit. In order for the PROs to be provided to the participant via the smartphone application on the day of the Early Termination Visit, site study staff will need to complete the End of Treatment form within the EDC system and select the reason for early termination. The completion of this form will notify the CRO to send the Early Termination PROs to the participant and discontinue any future notifications for PRO completion.

No new information will be collected from participants who withdraw from the study, except information collected in relation to the scheduled Withdrawal Visit or needed for the follow-up of adverse events (section 10.5).

The reason for withdrawal must be recorded in the eCRF.

For a participant who withdraws consent:

- if the participant withdraws consent during a visit and then agrees to it being the final visit, the investigator will complete the visit as a Withdrawal Visit and all the data collected up to and including that visit will be used
- if the participant withdraws consent during a telephone conversation, the investigator will ask the participant if they will attend a Withdrawal Visit. If the participant:
  - agrees to attend a Withdrawal Visit, all the data collected up to and including that visit will be used
  - refuses to attend an Early Termination Visit, the investigator should attempt to follow the participant's safety and future treatment; any information collected will only be recorded in the patient's medical records

If the participant explicitly requests that their data collected from the time of withdrawal of consent onwards not be used, this will be respected.

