11.2 Analysis Methodology for the Exploratory Endpoints

11.2.1 Estimand for the Number of Good Days (Week 1-4, 1-12, and 1-24) and Exploratory Endpoints

A summary of the intercurrent events that will be addressed and the estimand attributes can be found below.

The estimand is the difference in the mean weekly number of good days within each specified time interval between eptinezumab compared to other advanced preventive therapies (erenumab, fremanezumab, galcanezumab, or onabotulinumtoxinA) in adults with migraine on concomitant acute migraine therapy who have failed ≥ 2 prior oral preventive therapies and who are naïve to advanced migraine therapy based on a treatment policy strategy in which patients are analyzed according to the randomized group and are included in the analysis regardless of discontinuation or switching of the index migraine therapy during the follow-up period.

Intercurrent events that will be addressed include:

- Discontinuing the index preventive migraine medication with or without initiation of a new preventive therapy (i.e., a treatment switch).
- Withdrawal from the study due to lack of efficacy, adverse event, participant request, physician request, or loss to follow-up.
- Interruption or termination of infusions.

Attributes of the estimand for the number of good days include:

- The index treatment of interest is eptinezumab (100 mg or 300 mg) compared to other advanced preventive therapies (erenumab 70 mg or 140 mg, fremanezumab 225 mg or 675 mg, galcanezumab 120 mg, and onabotulinumtoxinA 155 units)
- The population is all patients with migraine who fulfil the inclusion and exclusion criteria.
- The primary endpoint of interest is the mean number of good days across weeks 1-12 after randomization
- The population-level summary is the mean difference between eptinezumab and other advanced preventive therapies for the endpoint

Estimands for the remaining exploratory endpoints can be formulated similarly to the estimand for the number of good days described above.

EQ-5D (weeks 1-4, 1-12, and 1-24)

- The endpoint to be obtained is the weekly EQ-5D score in each specified time interval
- The population level summary is the difference in mean weekly EQ-5D score in patients on eptinezumab relative to advanced migraine therapies in each time interval

PI-MBS (weeks 1-4, 1-12, and 1-24)

- The endpoint to be obtained is the weekly most bothersome symptom and associated severity

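### Withdrawing off-window switchers from the study, not only from treatment, undermines the treatment-policy estimand for them and exposes the switching endpoint

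*Protocol*

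**What the plan says.** **The withdrawal rule.** The rule in Protocol 6.1 covers "any participant wishing or needing to switch to an alternate medication outside of the study-specific guidelines for doing so". Such a person must leave the study itself, not only the study drug. A wish is enough; the switch need not have happened. Those who switch "in accordance with Section 6.3.1 will be permitted to remain in the study". Other prescribed migraine drugs do not trigger the rule: "There will be no restrictions on the use of other migraine related medications during the study period for acute or preventive treatment". It therefore concerns changes between advanced preventives. Protocol 6.3.1 and SAP 3.4 repeat it.

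**The windows (Protocol 6.3.1).**
- Subcutaneous (SC) anti-CGRP to another SC drug: any time once the previous injection's window is over.
- SC to eptinezumab or Botox: week 12 only.
- Eptinezumab or Botox to SC: not before week 12. "Participants who receive eptinezumab or Botox at week 12 (Visit 5) will not be permitted to switch their treatment" for the rest of the study.
- All arms: nothing after Visit 7.

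**After withdrawal.** Protocol 8.9: "No new information will be collected from participants who withdraw from the study", with exceptions for the Withdrawal Visit and adverse-event follow-up. One full set of Visit 8 eDiary assessments is requested at Early Termination, stored in the Visit 8 forms, and later prompts are switched off. Protocol 8.10 adds a safety contact eight weeks later.

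**What the analysis assumes.** SAP 11.2.1 has participants "included in the analysis regardless of discontinuation or switching of the index migraine therapy during the follow-up period". SAP 11.2.3 gives study withdrawal the same treatment-policy label and fills the gap by imputation. Protocol 5.5 states: "No participant will be withdrawn from the study due to non-compliance with treatment", because poor compliance is regarded as a real-world outcome.

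**The concern.** A treatment-policy estimand asks what happens to everyone randomised, including what follows a change of drug. It can be estimated only if outcomes after the change are collected. Here one class of changers is removed by rule at the moment the estimand most needs their data.

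People who want to change preventive early are likely to include poor responders, so their absence need not be random given the recorded data. The windows also differ by arm, so removal may differ by arm. Medication switching is itself one of the between-group objectives (Protocol section 2, item 8), and the same rule decides which wishes to switch can become recorded switches.

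**Working it through.** The documents give no expected rate of off-window switching, so there is no figure of the plan's to reproduce. The check compares the rules and then shows ranges under stated assumptions.

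**1. Do the passages fit together?**
- The mandatory-withdrawal list in Protocol 5.5 does not include off-window switching; 6.1 and 6.3.1 add it.
- SAP 3.3 defines withdrawal as termination of consent. A participant removed by protocol may not have terminated consent.
- SAP 11.2.3 analyses switchers who have endpoint data. Off-window switchers will have none after their exit visit.
- The mixed model (SAP 11.2.2) is valid for such gaps only under missing at random. The multiple imputation (SAP 11.2.6) states that assumption and draws only on the same randomised arm. Methods that penalise missing values are to be explored, not specified.

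**2. How unequal are the windows?** Inputs: follow-up 168 days; Visit 5 = Day 84; Visit 7 = Day 140; monthly = 28 days and quarterly = 84 days (Protocol 6.2). The treatment window is not defined, so I take it as one dosing interval.

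| Move | Open span | Share of 168 days |
|---|---|---|
| Monthly SC to SC | 140 − 28 = 112 days | 67% |
| Eptinezumab/Botox to SC, not re-dosed at Visit 5 | 140 − 84 = 56 days | 33% |
| Eptinezumab/Botox to SC, re-dosed at Visit 5 | 0 | 0% |
| Quarterly fremanezumab to SC, not re-dosed at Day 84 | 140 − 84 = 56 days | 33% |
| Quarterly fremanezumab to SC, re-dosed at Day 84 | 84 + 84 = 168, after Day 140: 0 | 0% |
| SC to eptinezumab/Botox | Visit 5 only | one visit |

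A monthly SC user who keeps to schedule has openings at the due dates, Days 28, 56, 84, 112 and 140, rather than on every day of the span.

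Everyone randomised to eptinezumab is under the tighter rule for moves to SC. In the pooled comparator, Botox is 1/(2+1) = one third of chronic migraine participants and none of the episodic ones. So 67% (all chronic) to 100% (all episodic) start under the SC rule.

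**3. Possible bias in a mean outcome.** Bias = (w_E − w_C) × D. Here w is the share removed in the eptinezumab (E) and comparator (C) arms, and D is how much worse removed participants do than their missing-at-random values, in SD units. All values are assumed.
- 5% vs 2%, D = 0.3: 0.03 × 0.3 = 0.009 SD.
- 10% vs 2%, D = 0.8: 0.08 × 0.8 = 0.064 SD.
- 15% vs 5%, D = 0.8: 0.10 × 0.8 = 0.08 SD.
- Reversed, 2% vs 5%, D = 0.8: −0.03 × 0.8 = −0.024 SD.

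Against the 0.36 in SAP Panel 6, the first three are 2.5%, 18% and 22%. That 0.36 refers to migraine days versus placebo, so it serves only as a yardstick.

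**4. Switching endpoint.** SAP 11.2.1 counts a switch when index therapy stops and a new therapy starts. SAP 18.9 treats unknown status with missing follow-up as still on index therapy. Assume 15% of each arm wish to switch, and one third of those wishes in the eptinezumab arm but two thirds in the comparator arm fall within the rules.
- Recorded switching: 0.15 × 1/3 = 5% vs 0.15 × 2/3 = 10%.
- Odds ratio: (0.05/0.95) ÷ (0.10/0.90) = 0.47, although the wish to switch is equal (odds ratio 1).
- Withdrawn: 10% vs 5%.

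Varying the wish over 10–20% and the accommodated shares over 1/3 vs 2/3, 0.5 vs 0.7 and 0.25 vs 0.9 gives odds ratios of 0.24 to 0.70. Swapping the arms in the first example gives 1/0.47 = 2.1.

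**The case against.** Several stronger readings are tempting, and the documents do not support them.

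- *All data stop.* They do not. Early Termination questionnaires, adverse-event follow-up and the safety contact remain. They describe the time of exit, however, not outcomes after the switch, and because they sit in the Visit 8 forms they could be mistaken for week-24 values.
- *The estimand is defeated.* It is not. In-window switchers stay, non-compliance alone removes nobody, and other prescribed preventives are unrestricted. Non-compliance and an off-window change of advanced preventive are also different events, so Protocol 5.5 and 6.1 are in tension rather than flat contradiction.
- *Eptinezumab and Botox participants can change only at week 12.* Those not re-dosed may move to SC from week 12 up to Visit 7. The week-12-only limit binds SC participants moving to eptinezumab or Botox.
- *The bias favours eptinezumab.* Botox belongs to the comparator, SC moves to eptinezumab or Botox are tightly limited, and quarterly fremanezumab narrows the SC window. Each of these can push the other way.
- *The size can be read from one arm.* Multiplying an assumed removal rate in the eptinezumab arm by an assumed shortfall sets comparator removal to zero and ignores that the models use each person's earlier weeks. The 15% used above also exceeds the under-10% total loss that SAP 15.1 leads one to expect.

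The study is also a pilot with no primary objective (Protocol 3.3). That lowers the stakes, but the SAP still tests most between-group outcomes at p<0.05 and names a main endpoint of interest over weeks 1–12, a period in which the windows already differ.

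**Conclusion.** The point holds in limited form. Off-window switchers must leave the study, their routine follow-up ends, and their post-switch outcomes, which the stated estimand requires, are replaced by model-based values under missing at random, with imputation from their own arm. For these participants the treatment-policy claim is undermined; for everyone else it stands.

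The rules bind the arms unequally, so differential removal is plausible. How many are removed, in which arm, and which way the result moves cannot be derived from the documents. The 0.009–0.08 SD range rests wholly on assumed removal rates and shortfalls, and its sign reverses if comparator removals are the larger. The switching endpoint is the more directly exposed: the same rules decide which switches can be recorded, and SAP 18.9, read literally, can score those removed for wanting to switch as non-switchers. The point merits correction, with medium confidence.

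**What to change.** Separate leaving study-provided treatment from leaving data collection.

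- **Protocol 6.1, 6.3.1, 8.9.** With consent, a participant who changes outside the windows stays in the existing eDiary and monthly calls to week 24. The date, drug and reason for the change are recorded.
- **SAP 3.3, 3.4, 11.2.3.** Reserve withdrawal for loss of consent or of contact, or define protocol-mandated withdrawal as its own category. Analyse these participants as randomised, using their observed outcomes.
- **SAP 18.9.** Count an off-window change as a switch. Do not default to index therapy when the recorded reason for exit is a wish to change drug.
- **Early Termination data.** Analyse at the actual date, not as week 24.
- **Those who decline further follow-up.** Specify a sensitivity analysis that does not rely on missing at random, and report their number by arm, week and reason. If participants have already been removed, this reporting is the minimum.

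Protocol 5.5 must be reconciled with 6.1, 6.3.1 and 8.9, and with the SAP sections above. Which switches to permit is a clinical rule for the sponsor; none is proposed here.

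Cost: a protocol clarification, SAP edits, and a few more app reports and calls per affected participant, using procedures already in place.

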## **10 Adverse Events**

### **10.1 Definitions**

#### **10.1.1 Adverse Event Definitions**

*Adverse event* – is any untoward medical occurrence in a patient or clinical study patient administered a medicinal product and which does not necessarily have a causal relationship with this treatment.

An adverse event can therefore be any un-favorable and unintended sign (including clinically significant out-of-range values from relevant tests, such as clinical safety laboratory tests, vital signs, ECGs), symptom, or disease temporally associated with the use of a medicinal product, regardless of whether it is considered related to the medicinal product.

It is Lundbeck policy to collect and record all adverse events, including pre-treatment adverse events, that is, those that start after the patient has signed the *Informed Consent Form* and prior to the first dose of IMP.

*Serious adverse event* – is any adverse event that:

- results in death
- is life-threatening (this refers to an event in which the patient was at risk of death at the time of the event; it does not refer to an event that hypothetically might have caused death had it been more severe)
- requires inpatient hospitalization or prolongation of existing hospitalization
- results in persistent or significant disability/incapacity
- is a congenital anomaly/birth defect

is medically important (this refers to an event that may not be immediately life-threatening or result in death or hospitalization, but may jeopardize the patient or may require intervention to prevent any of the SAEs defined above)

Examples of medically important events are intensive treatment for allergic bronchospasm; blood dyscrasia or convulsions that do not result in hospitalization; or development of drug dependency or drug abuse.

Planned hospitalizations or surgical interventions for a condition that existed before the patient signed the *Informed Consent Form* and that did not change in intensity are not adverse events. Emergency room visits that do not result in admission to the hospital are not necessarily SAEs; however, they must be evaluated to determine whether they meet any of the SAE definitions (for example, life-threatening or other serious [medically important] event).

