### **10.3 Recording Adverse Events**

Adverse events (including pre-treatment adverse events) and adverse drug reactions must be recorded on an *Adverse Event Form*. The investigator must provide information on the adverse event / drug reaction, preferably with a diagnosis, or at least with signs and symptoms; start and stop dates; intensity; causal relationship to the IMP; action taken; and outcome. If the adverse event is not related to the IMP, an alternative etiology must be recorded, if available. If the adverse event is an overdose, the nature of the overdose must be stated (for example, medication error, accidental overdose, or intentional overdose). If the intensity changes during the course of the adverse event, this must be recorded on the *Adverse Event Form*.

If the adverse event is *serious*, this must be indicated on the *Adverse Event Form*. Furthermore, the investigator must report the SAE to Lundbeck immediately (within 24 hours) after becoming aware of it (see section [10.4](#)).

If individual adverse events are later linked to a specific diagnosis, the diagnosis should be reported and linked to the previously reported adverse events.

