### 16.3 Safety Analyses

#### 16.3.1 Analysis of Adverse Events

Adverse event and adverse drug reaction data will be tabulated and reported. No additional analyses are planned.

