Adverse events will be recorded according to MedDRA system organ class and preferred term by therapy group and classified as pre-treatment adverse events (an adverse event that starts on or after the date the patient signed the Informed Consent Form and prior to the date and time of first dose of therapy) or treatment-emergent adverse events (TEAE; an adverse event that starts or increases in intensity on or after the date and time of first dose of therapy). Only TEAEs will be reported and will be tabulated as:

- Any AEs
- AEs probably related to the therapy received stratified by AE
- Severe AEs stratified by AE
- AE leading to treatment discontinuation stratified by AE
- Serious AE stratified by AE
- Serious AE probably related to the therapy received by AE
- Serious AE leading to treatment discontinuation stratified by AE
- Fatal AE
- Overall AEs
 - Any SAE
 - Any AE probably related to the therapy received
 - Any Severe AE
 - Any AE leading to treatment discontinuation
 - Any serious AE
 - Any serious AE probably related to the therapy received
 - Any serious AE leading to treatment discontinuation
 - Fatal AE

13 Data Reviews

Data quality is controlled throughout the study by study-specific edit checks programmed within the software platforms used to collect data (eCaseLink and eCaseLinkMe).

Edit checks are separated into the following categories:

- Programmed edit checks primarily checks programmed within the EDC system that allow for data to be checked in real time during the data entry process, and which assist sites during data entry. These checks may be divided into:
 - Database Check: The corresponding data field limits the entry to a specific format (e.g. time in “HH:MM” [hours:minutes]).
 - Programmed Soft Check: This check category allows a confirmation of the discrepant information and subsequent manual closing of the discrepancy by Xcenda.
 - Programmed Hard Check: This check category requires a correction of the entered value to close the discrepancy.
- Manual edit checks: Checks that are not pre-programmed within the EDC system and are performed by appropriate Lundbeck and/or Xcenda study personnel. Manual checks may

result in the need for manual queries to be recorded by Xcenda within the EDC system for site response and/or data correction.

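### Lack of efficacy behind a medication switch is routed to the adverse event form, and the SAP's AE summary rows do not separate it from tolerability

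*Protocol*

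**What the plan says.** Protocol section 6.1 covers changes of preventive treatment. It has the coordinator look into the reason for any change and record it in the CRF, and then adds: "Any adverse events identified as the cause of a medication switch (e.g. lack of efficacy) will be reported according to Section 10.3". Section 10.3 requires entry on the adverse event form. The definition in section 10.1.1 is broad: an adverse event "is any untoward medical occurrence in a patient or clinical study patient administered a medicinal product". It neither names nor excludes lack of efficacy. Section 16.3.1 states only that "Adverse event and adverse drug reaction data will be tabulated and reported".

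SAP section 12 defines a treatment-emergent event by timing or worsening alone: "an adverse event that starts or increases in intensity on or after the date and time of first dose of therapy". It plans a table of "AE leading to treatment discontinuation stratified by AE", and overall rows for any AE and any AE leading to treatment discontinuation. No line or rule deals with lack of efficacy. Events are coded by MedDRA system organ class and preferred term, and reported descriptively by therapy received.

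SAP section 11.2.1 keeps the two ideas apart in its list of intercurrent events: "Withdrawal from the study due to lack of efficacy, adverse event, participant request, physician request, or loss to follow-up".

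**The concern.** A site that follows section 6.1 files an adverse event when a participant changes drug because migraine is not controlled. A site that works from section 10.1.1 alone may not. In the first case the entry meets the SAP's timing rule and is counted in the overall AE row. If a switch counts as discontinuation, it is also counted in the AE-discontinuation row.

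That last row is normally read as a measure of tolerability, and the SAP's safety objective is the safety and tolerability of eptinezumab. With efficacy failures in it, the row measures something else. The same event would also count in the medication-switching endpoint, so one occurrence would appear as both an effectiveness finding and a safety finding.

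The route to the form is also selective. Section 6.1 sends lack of efficacy there only when it causes a switch, and the opportunity to switch depends on the product.

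**Working it through.** The plan gives no figure on this point, so there is none to reproduce. The check traces the text and then asks whether the documents allow a size to be put on the effect.

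**1. Route to the tables.** Protocol 6.1 names lack of efficacy as an example of an adverse event behind a switch. Protocol 10.3 puts it on the adverse event form. SAP 12 counts any event starting or worsening after first dose. Nothing along this route removes or separates it.

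**2. Does a switch count as discontinuation?** SAP 12 does not define treatment discontinuation. The nearest wording is the intercurrent event in SAP 11.2.1: "Discontinuing the index preventive migraine medication with or without initiation of a new preventive therapy (i.e., a treatment switch". On that wording a switch is a discontinuation of the index drug. This is an inference carried from one section to another.

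**3. Switch timing (protocol 6.3.1, with dosing intervals from 6.2).**
- Monthly SC products: a change to another SC product is allowed once each injection's window has ended, and none after Visit 7 (Day 140). Windows end on Days 28, 56, 84, 112 and 140, which gives 5.
- Eptinezumab and Botox: no move to an SC product before week 12, and no switch after a second dose at week 12. For a participant on schedule this gives 1, at Day 84.
- Quarterly fremanezumab (84-day interval): 1, at Day 84.
- A switch wanted outside these rules leads to withdrawal, where lack of efficacy can be recorded as the withdrawal reason.

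**4. What unequal timing could do.** Assume the same chance p of an efficacy-driven switch at every window, independent between windows. The share with at least one such entry by week 24 is 1 − (1 − p)^k, where k is the number of windows. The values of p are assumed.

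| Assumed p | k = 1 | k = 5 |
|---|---|---|
| 1% | 1.0% | 4.9% |
| 2% | 2.0% | 9.6% |
| 5% | 5.0% | 22.6% |
| 10% | 10.0% | 41.0% |

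These are upper-end illustrations of the timing rules acting alone.

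**5. Direction.** If p is allowed to differ, the order can reverse. With 10% at a single window against 1% at each of five, the same table gives 10.0% against 4.9%.

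**6. Effect on the discontinuation row.** Let b be tolerability discontinuations per 100 and e efficacy-driven switches per 100, with no overlap. The row is inflated by (b + e)/b. With b = 3 assumed, e = 5 gives 8/3 = 2.7 and e = 20 gives 23/3 = 7.7. With b = 10 assumed, the same e gives 15/10 = 1.5 and 30/10 = 3.0. The result depends entirely on b and e, and neither is in the documents.

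**The case against.** The strongest reply is that the planned tables do not hide the problem. Because SAP 12 codes by preferred term and stratifies the discontinuation table by event, a lack-of-efficacy entry would normally appear under its own term, where a reader could subtract it. This largely stands and limits the mixing to the summary rows. It does depend on sites entering lack of efficacy as the term. Section 10.3 prefers a diagnosis, so some sites might enter migraine instead.

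Second, the line quoted from SAP 11.2.1 concerns withdrawal from the study, whereas protocol 6.1 concerns a switch by someone who may stay in. That is fair: the passages are inconsistent in how they classify lack of efficacy, but they do not contradict each other on the same event. Logging lack of efficacy may also be a deliberate choice, given the broad definition and the sponsor's policy of recording all adverse events. The documents do not settle this. It is a reason to offer separate display as an alternative to taking lack of efficacy off the form.

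Third, a reader might infer that the comparator arm would look less safe simply because SC users can switch more often. The documents do not support that. Events are reported by therapy received, not by randomized group, and no between-group safety test is planned. Botox and quarterly fremanezumab share the later switch timing. Section 6.1 also covers changes to other preventives, which are open to every group if prescribed. Protocol 16.2 restricts the safety population to eptinezumab recipients while the SAP uses all treated patients, so even which groups will be tabulated needs reconciling.

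**Conclusion.** The point holds in a limited form. As written, protocol 6.1 classes lack of efficacy behind a switch as an adverse event, and SAP 12 would carry it into the overall AE row and, if a switch counts as discontinuation, into the overall AE-discontinuation row. Those rows would then mix efficacy failure with tolerability and overlap with the switching endpoint. The term-level tables would largely remain readable.

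Because capture depends on a switch, and switch timing differs by product, capture may differ between therapies received. Neither size nor direction can be determined: the documents give no rates, and direction turns on true failure rates, product mix and how withdrawals are coded. All percentages and multiples in the working are illustrations under assumed inputs. In an exploratory study with descriptive safety tables this is a moderate point, worth correcting because the correction costs almost nothing.

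**What to change.** Reconcile protocol 6.1 with SAP 11.2.1 and 12. The simplest way is to remove lack of efficacy as the example in 6.1 and record it in the eCRF as the reason for switch or withdrawal. Section 6.1 already requires the reason for change to be recorded, so no information is lost. A separate untoward medical event would still be reported as an adverse event.

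If the sponsor prefers to keep lack of efficacy on the form, SAP 12 should:
- flag these entries and show them as their own line;
- present the AE summary and AE-discontinuation rows with and without lack-of-efficacy terms;
- add a separate table of switch reasons by group.

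In either case SAP 12 should state whether a switch counts as treatment discontinuation. The cost is one protocol phrase, a sentence or two in the SAP, and one or two extra table rows, plus the switch-reason table if that option is taken. The switching endpoint is unaffected.
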